9.7 Data collection

We will collect and enter all patient and caregiver-reported data electronically using Research Electronic Data Capture (REDCap). The REDCap Survey is a tool for building and managing online surveys. Vanderbilt University, in collaboration with a consortium of institutional partners, has developed this software and workflow methodology for electronic collection and management of research and clinical trial data. Our research team has extensive experience using REDCap and will create and design the surveys in a web browser, with institutional information technology support. The REDCap Survey system offers secure, HIPAA compliant, web-based applications that provide an intuitive interface for participants to enter data, with real-time validation rules at the time of entry.

Participants will use tablet computers to complete questionnaires during hospitalization or in clinic. If any participants refuse or are unable to complete the questionnaires on the computer, they will be permitted to use hard-copy paper versions. Participating caregivers who are not present in the hospital during the period of data collection will be provided with remote access to the REDCap system [Appendix L], paper-based questionnaires for home administration [Appendix K], or administration of questionnaire over the phone [Appendix M]. The RA will contact patients (in person), and caregivers (in person or via telephone) daily for two days to remind them to complete and return the surveys. If study participants fail to complete the surveys within two days of the expected time point, we will report the data as missing and document the reason for incompleteness. Table 4 details the schedule for administering the self-report measures. All participants (patients and caregivers) will complete baseline evaluation within 72 hours of study enrollment (excluding public holidays, in which case the RA will approach in 96 hours). All participants will then have a second evaluation during their second week of hospitalization for HCT. Patients undergoing autologous HSCT (and their caregivers) will have their second evaluation during the hospitalization on day +5 (48 hour window: day +5 to day +7). Patients undergoing allogeneic HCT (and their caregivers) will have their second evaluation during the hospitalization on day +8 (48 hour window: day +8 to day +10). We have chosen these time points carefully to assess patients during their hospitalization at the peak of severity in symptoms based on the type of transplant being performed. All patients (and caregivers) will also complete additional questionnaires at 3, 6, and 12 months post-transplantation (+/- 2 week window).

Table 4: Administration of Self-Report Measures

Participant	Baseline	Week-2:(Day+5 auto, day +8 allo)	3, 6, & 12 months (+/- 2 week window)
Patient Measures:			
Demographics	X		
FACT-BMT/Fatigue	X	X	X
ESAS	X	X	X
HADS	X	X	X
PHQ-9	X	X	X
PCL (PTSD)	X	X	X
Brief Cope	X	X	X
Caregiver Measures:			
Demographics	X		
CarGOQOL (QOL)	X	X	X
HADS	X	X	X
PHQ-9	X	X	X
Brief Cope	X	X	X

10.0 Data and Specimen Banking: Not applicable

10.1 Data analysis

Specific Aim 1: To demonstrate the efficacy of inpatient integrated palliative and transplant care for improving patient-reported outcomes: Analyses will begin with descriptive and graphical summaries of the endpoints and evaluation of whether a normality assumption is reasonable for the endpoint or whether transformation is necessary. All statistical tests will be two-sided with an alpha level of 0.05. For all secondary and exploratory outcomes, we will use the false discovery rate (FDR) control method to address the issue of multiple testing. We selected an FDR of 0.15, which denotes the acceptable percentage of results that potentially represent false positives.⁶² The primary endpoint of the study will be to compare patient QOL (FACT-BMT) scores at week-2 between the study groups controlling for baseline values and demographic and clinical factors (as necessary for any imbalances in baseline variables) using a linear regression model. We will also compare secondary endpoints including patients' symptoms (ESAS), fatigue (FACT-Fatigue), depression and anxiety symptoms (HADS and PHQ9), and coping (Brief Cope) at week-2 between the study groups using linear regression models controlling for baseline values and clinical factors (as necessary for any imbalances in baseline variables). In the event that the effect of the intervention differs by transplant type, conditioning intensity, or other patient characteristics, we will examine these variables as interaction terms in the linear regression analyses. Finally, we will compute the effect size and Reliability Change Index to assess practical and clinical significance in the degree of change in the primary and secondary outcomes.

We will also utilize linear mixed models of the longitudinal data, allowing us to account for dependency among means over time and to control for demographic and clinical factors (as necessary for any imbalances in baseline variables) when examining change between groups in outcomes of interest across multiple time points (i.e., baseline, 2 weeks, 3, 6, and 12 months post-HCT). We will estimate practical and clinical significance of these outcomes (Cohen's d and Reliability Change Index).

Specific Aim 2: To assess the impact of inpatient integrated palliative and transplant care on caregiver-reported QOL and psychological outcomes: We will similarly compare caregivers' QOL

PROTOCOL TITLE: Multi-Site Randomized Trial of Inpatient Palliative Care for Patients with Hematologic Malignancies Undergoing Hematopoietic Stem Cell Transplantation

(CARGOQOL), depression and anxiety symptoms (caregivers HADS and PHQ9), and coping at week-2 using linear regression models controlling for baseline values and clinical factors (as necessary for any imbalances in baseline variables). We will also use linear mixed models of the longitudinal data, allowing us to account for dependency among means over time and to control for demographic and clinical factors (as necessary for any imbalances in baseline variables) when examining change between groups in outcomes of interest across multiple time points (i.e., baseline, 2 weeks, 3, 6, and 12 months post-HCT). We will again estimate practical and clinical significance of these outcomes (using Cohen's d and Reliability Change Index).

Specific Aim 3: To explore mediators and moderators of the effect of the palliative care intervention on patient-reported QOL: We will conduct bootstrapped tests of mediation to determine whether group differences in patient-reported QOL (FACT-BMT) are mediated by improved symptom burden (mediators: ESAS/HADS), or coping (mediator: Brief Cope). Although in our randomized trial, we did not identify moderators of the effect of the palliative care intervention, we will test for potential moderators to ensure generalizability of our findings, as other studies have found age and gender as moderators of the impact of palliative care in patients with lung cancer.⁶³ We will create interaction terms for the linear regression analyses and linear mixed models to examine whether differences in patient-reported QOL are moderated by patient factors (age, gender, race), transplant factors (type of HCT, conditioning intensity), or study site.

Missing Data: The analyses will initially focus on the study completers to estimate the effect of the integrated palliative care intervention in patients undergoing HCT (and their caregivers) who completed the protocol as intended without imposing assumptions about missing data. We will also use the intention-to-treat principle with all randomized subjects, conducting sensitivity analyses to explore how various assumptions about missing data and differences between completers and non-completers affect the estimated outcomes. If data appear to be missing at random, we will employ multiple imputation methods⁶⁴, maximum likelihood estimate approach with EM algorithm⁶⁵, and mixed-effects modeling⁶⁶ that can adequately account for data missing at random. However, if we find that participants do not complete the study because of disease worsening, suggesting missing data are not random, we will employ pattern mixture modeling or joint modeling approaches⁶⁷ to handle incomplete data, and perform sensitivity analysis⁶⁸ to assess the impact of missing data.

10.2 Sample Size Calculation & Power Analysis:

Although we observed a large effect size for our palliative care intervention on patient-reported QOL during hospitalization (primary endpoint, Cohen's d = 2.9), we chose to be conservative in estimating the sample size for this trial given the proposed testing of the effect of the intervention on caregivers and post-HCT outcomes, expected attrition over time, and the proposed tests of mediation and moderation. In our prior study, we observed a 6.9 point difference (SD = 20) in QOL at week-2 between intervention and control group. With a sample size of 360, we will have 87% power to detect at least 6.9 point difference in patient QOL at week-2 between groups with a two-sided 0.05 significance level and assuming 10% missing data at week-2. Importantly, we only had 2% and 6.9% missing data at week-2 and 3-months post-HCT in our prior study. With a sample size of 360, we will also have > 80% power to detect a treatment difference in secondary patient-reported outcomes at week-2 (symptom burden, depression, and anxiety) with a two-sided 0.05 significance level. Assuming a missing data rate of 15% at three and six months, we will have 80% power to detect a 4.3 point difference in patient-reported QOL at 3 and 6 months post-HCT between the two groups (based on the difference we detected in our previous study). In our prior trial, we enrolled 94 (56%) caregivers and we noted a 1.6-point difference (SD = 3.3) in caregiver HADS-depression scores between the two study groups at week-2. Assuming that we enroll caregivers

PROTOCOL TITLE: Multi-Site Randomized Trial of Inpatient Palliative Care for Patients with Hematologic Malignancies Undergoing Hematopoietic Stem Cell Transplantation

for 50% of the patients included in this study (n = 180), we will have 90% power to detect a 1.6-point difference in caregiver HADS-depression scores at week-2 between the two groups with a two-sided 0.05 significance level.

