3.0 Inclusion and Exclusion Criteria

We propose a multi-site randomized controlled trial of inpatient integrated palliative and transplant care versus transplant care alone in 360 patients with hematologic malignancies hospitalized for HCT and 180-360 of their caregivers. Patients will be recruited from the MGH Cancer Center, Fred Hutchinson Cancer Research Center, and Duke University. Patients will be randomized in 1:1 fashion and stratified by study site and transplant type (autologous vs. allogeneic). As autologous and allogeneic HCT have significantly different courses of recovery post-transplant,¹ we will stratify by the type of transplant to ensure adequate and balanced representation between the two study groups.

3.1 Screening Procedures:

All participating sites have an admission database which includes all planned HCT admissions. The site PIs will grant the research assistant (RA) at that site access to the database to review the weekly list of scheduled admissions for transplant to screen for eligible patients. Transplant admissions are always scheduled in advance, thus our screening method will ensure we identify all patients who are eligible for

PROTOCOL TITLE: Multi-Site Randomized Trial of Inpatient Palliative Care for Patients with Hematologic Malignancies Undergoing Hematopoietic Stem Cell Transplantation

study participation. We utilized these study procedures in our prior single center trial and enrolled 86% of potentially eligible participants.

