For registration of patients from DF/HCC institutions, study staff will complete the DF/HCC protocol-specific eligibility checklist using the eligibility assessment documented in the participant's medical record and/or research chart. Study staff will confirm that the participant meets all inclusion criteria as described in this protocol and the criteria on the eligibility checklist.

Patients from other investigative sites will be entered on the study centrally by MGH study staff. Study staff from the participating institution will confirm eligibility criteria and fax or email the following documents to study staff at MGH: deidentified signed consent form/s, and a completed eligibility checklist. MGH study staff will follow DF/HCC Standard Operating Procedure for Human Subject Research Titled *Subject Protocol Registration* (SOP #: REGIST-101) and register the participant on the protocol. Once the patient has been registered, a member from of the MGH Cancer Outcomes Research Program (CORE) team (independent from the study staff) will perform randomization procedures using a computer-generated randomization schema, stratified by study site and transplant type. MGH study staff will fax or e-mail the information about randomization to the study staff at the participating site. MGH study staff may also call the research nurse or data manager at the participating site to verbally confirm registration and randomization.

5.2 Site Investigators and Study Staff Training:

We will conduct an in-person centralized training at MGH for the site lead investigators (site PIs) and RAs to ensure consistent recruitment and enrollment procedures across study sites. We will train the investigative team on: 1) identifying potentially eligible patients via the admission database; 2) tracking potentially eligible patients until their admission for HCT; 3) communicating with oncology clinicians about patient eligibility; 4) obtaining written informed consent from patients and caregivers; and 5) monitoring patients and caregivers longitudinally and administering study questionnaires. Additionally, the site lead investigators will attend the palliative care training described below in-person during their MGH visit.

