9.0 Procedures Involved

9.1 Study design

We propose a multi-site randomized controlled trial of inpatient integrated palliative and transplant care versus transplant care alone in 360 patients with hematologic malignancies hospitalized for HCT and 180-360 of their caregivers. Patients will be randomized in 1:1 fashion and stratified by study site and transplant type (autologous vs. allogeneic). As autologous and allogeneic HCT have significantly different courses of recovery post-transplant,¹ we will stratify by the type of transplant to ensure adequate and balanced representation between the two study groups

9.2 Palliative Care Intervention:

Patients randomized to the palliative care intervention will meet with a palliative care clinician within 48 hours of randomization (excluding weekends). After the initial visit, the palliative care clinicians will meet with patients at least two times per week during their hospitalization. Patients, caregivers, or the palliative care clinician may initiate additional visits as needed.

Table 2: Palliative Care Intervention Domains		
Domain	Elements	Key Points
Therapeutic Relationship	
 • Introducing role palliative care • Understanding the patient and caregiver experience • Building trust with the patient and caregiver 	
 • Develop a strong therapeutic relationship with patients and caregivers • Learn about the values, life goals, and experiences of patients and their caregivers both prior to and after the cancer diagnosis • Develop trust and credibility with patients and caregivers by providing reassurance and outlining parameters of communication

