	
 • Supporting caregiver coping • Providing referral for additional support 	
 • Bolster caregiver coping by assessing burden, enhancing their communication with patients, and recommending additional support • Involve other members of the team for patients and caregivers who may be experiencing severe distress (e.g., social work, psychology)
--	--	---

As shown in Table 2 above, the palliative care intervention will focus on the following content areas: 1) addressing patients' physical and psychological symptoms; 2) managing patients' and caregivers' expectations; and 3) providing patients and caregivers with strategies to cope with the illness during HCT. Palliative care clinicians will focus specifically on symptoms we have shown to be prevalent in this population, including nausea, pain and mucositis, fatigue, sleep disturbances, constipation, diarrhea, anxiety and depression.

Ensuring Fidelity of the Palliative Care Intervention: We will take several steps to ensure the fidelity of our study design, training, and intervention delivery as noted in the table below (Table 3). Specifically, for the study design, we will utilize an evidence-based palliative care intervention guide, measure the number and duration of palliative care visits, and monitor the number of participants in the control arm receiving palliative care. Also, we will employ rigorous training procedures with in-person training for site PIs and RAs; and monthly telephone conferences with Drs. [name] and [name] with the site PIs and palliative care clinicians to discuss any issues. To ensure the fidelity of the intervention delivery, we will review palliative care clinicians' documentation to enable us to assess the content of the clinical encounter. Drs. [name] and [name] will independently review electronic surveys completed by the palliative care clinicians to ensure intervention fidelity and conformity between sites in addressing the domains and topics as specified by the guide. Based on this review, Drs. [name], [name], and [name] will provide constructive feedback as needed to individual clinicians to ensure they are delivering the intervention in a consistent fashion. The site PIs will also review palliative care notes in the health record to ensure adherence to the intervention guide content and provide feedback to clinicians at the site research meetings.

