As done in our prior trial,³⁴ patients randomized to the transplant care alone arm will not meet with palliative care clinicians, though they may consult with palliative care at their request or at the discretion of their treating clinicians. In most transplant centers, supportive care measures are instituted at the discretion of the transplant oncology team and include symptom-directed therapies for nausea, pain, and diarrhea. Additionally, social workers are occasionally available to assist in helping patients and families emotionally during the HCT process. We will collect data on social work consultations and consider them as a covariate in our analyses. Patients randomized to transplant care alone will receive all supportive care measures as instituted by the transplant oncology team including social work consultations upon request. We anticipate minimal cross contamination, as the rate of palliative care consultation is less than 5% for patients admitted for HCT at our participating sites. In our prior single center trial, only two patients randomized to transplant care alone received palliative care consultations. Notably, the palliative care intervention did not lead to significant changes in supportive care practices implemented by the transplant clinicians. While patients undergoing HCT often interact post-transplant, they are typically isolated during the acute hospitalization period and have minimal interactions. Patients are also typically seen by multiple providers including nutritionists, physical therapists, residents, nurse practitioners, and social workers. Consequently, patients randomized to transplant care alone will not notice the lack of interaction with palliative care clinicians. Therefore, we do not anticipate that cross-contamination will be a significant issue in the proposed trial.

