9.4 Selection of Instruments

We selected instruments based on our prior studies and the conceptual framework of our intervention, which seeks to improve patients' and caregivers' QOL and mood, reduce their symptom burden, and enhance their coping strategies, which will ultimately lead to improvement in their QOL and psychological outcomes post-HCT.

- **Demographics:** Patients and caregivers will complete a demographic questionnaire at baseline detailing their age, sex, race, ethnicity, religion, relationship status (caregivers will specify their relationship with patients), educational level, annual household income, and living situation [appendix A].
- **QOL-Patient:** We will use the Functional Assessment of Cancer Therapy-Bone Marrow Transplant (FACT-BMT) to assess QOL, which has been validated for use in patients undergoing HCT.⁵³ The FACT-BMT consists of four subscales assessing well-being across four domains (physical, functional, emotional, and social), as well as additional questions specific to the transplant population. These self-reported measures possess strong psychometric properties and have been validated for patients with leukemia [appendix B].
- **Symptoms-Patient:** We will administer the revised Edmonton Symptom Assessment Scale (ESAS) to assess various symptoms relevant to this population. The revised Edmonton Symptom Assessment Scale has been well validated and extensively studied in patients with cancer undergoing active chemotherapy treatment [Appendix C]⁵⁴.
- **QOL-Caregiver:** We will use the CareGiver Oncology QOL questionnaire (CarGOQOL) to measure caregiver QOL. The CarGOQOL is a 29-items well-validated instrument to measure QOL in multiple domains.⁵⁵ The CarGOQOL has been previously

PROTOCOL TITLE: Multi-Site Randomized Trial of Inpatient Palliative Care for Patients with Hematologic Malignancies Undergoing Hematopoietic Stem Cell Transplantation

validated for caregivers of patients with cancer including hematologic malignancies [Appendix D]

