- **Mood (patient & caregivers):** We will use the Hospital Anxiety and Depression Scale (HADS) to assess symptoms of depression and anxiety in all study participants (patients and caregivers). The HADS is a 14-item questionnaire that contains two 7-item subscales assessing depression and anxiety symptoms during the past week [appendix E]⁵⁶. Used extensively in samples of patients with cancer and their caregivers, the questionnaire consists of a four-point item response form that quantifies the degree to which participants experience mood symptoms. Scores on each subscale range from 0 to 21, with a cutoff of 8 or greater denoting clinically significant anxiety or depression. We will also use the PHQ-9 to assess major depressive syndrome in study participants. The PHQ-9 is a nine-item measure that evaluates symptoms of major depressive disorder according to the criteria of the diagnostic and statistical manual of mental disorders-IV [appendix F]⁵⁷.
- **PTSD symptoms - Patient:** We will use the Post-Traumatic Stress Disorder Checklist (PCL) to assess symptoms of post-traumatic stress in patients. The PCL is a 17 item self-reported measure that evaluates symptoms of post-traumatic stress disorder according to the criteria of the Diagnostic and Statistical Manual of Mental Disorders-IV [Appendix G].³⁹
- **Fatigue – Patient:** we will use the 13-item FACT-Fatigue scale to assess fatigue symptoms [appendix H].⁵⁸
- **Coping strategies (patient and caregiver):** We will use the Brief Cope, a 28-item questionnaire that assess 14 methods of coping (e.g., self-distraction, humor, denial) using a 4-point Likert scale [appendix I].⁵⁹

9.5 *Data from the Electronic Health Record:*

Study staff will collect clinical, disease, and transplant characteristics at baseline including: ECOG Performance Status at the time of HCT, clinical comorbidities as measured by the HCT-Comorbidity Index,⁶⁰ underlying diagnosis, date of diagnosis, disease status at the time of HCT, disease risk based on the Disease Risk Index,⁶¹ conditioning regimen, donor type, donor source, date of HCT, and hospital length-of-stay. We will also collect data on the incidence and severity of acute and chronic graft-versus-host disease and the incidence of relapse at one year post-HCT as these outcomes are associated with QOL.

9.6 *Data on Palliative Care Visits:*

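### The primary week-2 FACT-BMT model does not plan the stratification factors as main effects, and the plan does not clearly keep social work consultations out of it

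*Combined protocol and SAP*

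**What the plan says.** **Primary model.** One sentence in Section 10.1 (Specific Aim 1) defines it: week-2 FACT-BMT is compared between arms "controlling for baseline values and demographic and clinical factors (as necessary for any imbalances in baseline variables) using a linear regression model". Baseline FACT-BMT is the only covariate fixed in advance. The candidates for imbalance-driven adjustment come from Sections 9.4 and 9.5: a "demographic questionnaire at baseline detailing their age, sex, race, ethnicity, religion, relationship status" and further items, and a chart review ("Study staff will collect clinical, disease, and transplant characteristics at baseline including: ECOG Performance Status at the time of HCT" and others). No list, test or threshold is given.

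**Randomisation.** Section 9.1 states: "Patients will be randomized in 1:1 fashion and stratified by study site and transplant type (autologous vs. allogeneic". Section 3.0 says the same, and Section 5.1 describes a "computer-generated randomization schema, stratified by study site and transplant type". Section 21.0, describing the same step, mentions study site alone. No section says whether assignment is blocked within strata. The reason given for stratifying by type is prognostic: "As autologous and allogeneic HCT have significantly different courses of recovery post-transplant".

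**Role of the strata in the analysis.** Transplant type appears in Aim 1 as an interaction term, should the effect differ by type, and in Aim 3 as an exploratory moderator. Site appears only as a moderator in Aim 3. Neither is planned as a main effect in the primary comparison.

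**Social work.** Section 9.3 states: "We will collect data on social work consultations and consider them as a covariate in our analyses". It does not say which analyses. Table 2 in Section 9.2 tells palliative care clinicians to "Involve other members of the team for patients and caregivers who may be experiencing severe distress (e.g., social work, psychology", among others.

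**The concern.** There are two separate issues.

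1. **Strata left out.** Blocked stratified randomisation removes between-stratum variation from the true sampling error of the arm difference. A model that ignores the strata leaves that variation in its residual variance. The standard error is then overstated, the interval too wide and the test conservative. The imbalance rule does not rescue this, because it selects factors that differ between arms and stratification is meant to prevent exactly that. The factor the protocol itself singles out as important is therefore among the least likely to enter.

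2. **A post-randomisation covariate.** Consultations happen during the stay and can follow randomisation. If they mark distress, and the intervention changes how often they occur, conditioning on them mixes a consequence of assignment into the treatment effect. The resulting bias could go in either direction.

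**Working it through.** **Inputs from the documents (Section 10.2):** difference 6.9 points, SD 20, 360 patients, 10% missing at week 2, two-sided 0.05. Evaluable: 360 × 0.90 = 324, or 162 per arm.

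**Assumed, because the documents give no figure:** correlation r of baseline with week-2 FACT-BMT (0 or 0.5); share R of the variance left after baseline that the strata explain (5, 10 or 20%); blocking within strata.

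**Step 1: the plan's power.** SE = 20 × √(2/162) = 2.222. Then 6.9/2.222 = 3.105, and power = Φ(3.105 − 1.96) = 87.4%. The stated 87% reproduces as an unadjusted two-sample comparison.

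**Step 2: would an imbalance rule pick up transplant type?** Take six strata of 54 and blocks of 4. The arms can then differ by at most 2 patients in a stratum (28 v 26). If all three autologous strata lean one way and all three allogeneic strata the other, the arms have 84/162 v 78/162 autologous. z = 0.0370/√(0.25 × 2/162) = 0.0370/0.0556 = 0.67, p about 0.50. Even this worst case is not flagged at p<0.05 or p<0.10. In 8,000 simulated trials of this layout, neither type nor site was ever flagged. With simple randomisation each was flagged in about 5% at p<0.05.

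**Step 3: effect of omitting the strata under blocking.** Let k = √(1 − R). The reported SE is 1/k times the true one.
- Excess interval width = 1/k − 1.
- Type I error = 2(1 − Φ(1.96/k)).
- Power with strata omitted = Φ((NCP − 1.96)/k); with strata included = Φ(NCP/k − 1.96).
- NCP = 3.105 for r = 0. For r = 0.5, SE = 2.222 × √0.75 = 1.925 and NCP = 6.9/1.925 = 3.585.

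| R | k | Interval too wide by | Type I error | Power omitted → included, r = 0 | Same, r = 0.5 |
|---|---|---|---|---|---|
| 5% | 0.975 | 3% | 4.4% | 88.0 → 89.0% | 95.2 → 95.7% |
| 10% | 0.949 | 5% | 3.9% | 88.6 → 90.5% | 95.7 → 96.6% |
| 20% | 0.894 | 12% | 2.8% | 90.0 → 93.5% | 96.5 → 98.0% |

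The loss is 1.0, 1.9 or 3.5 points of power at r = 0, and 0.5, 0.9 or 1.4 points at r = 0.5. No entry falls below the stated 87%.

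**Step 4: social work consultations.** If consulted patients differ in score because they are more distressed, adjustment shifts the estimate by about (score gap of consulted patients) × (arm difference in consultation rate). Neither factor is in the documents. As an illustration, a 6-point gap and a 10-percentage-point rate difference give 6 × 0.10 = 0.6 points, which is 0.6/6.9 = 9% of the design difference. With SE 1.925 the standardised shift is 0.6/1.925 = 0.312. Type I error is Φ(−1.96 + 0.312) + Φ(−1.96 − 0.312) = 0.050 + 0.012, about 6%. If the rates do not differ between arms, the shift is zero.

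**The case against.** **On social work, the strongest reply is textual.** Section 10.1 limits added covariates to those needed for imbalances in baseline variables, and a consultation after randomisation is not one. Section 9.3 only says they will be considered. It also reports that the intervention did not significantly change transplant clinicians' supportive care practices in the prior trial, and it describes social workers as only occasionally available. A reader might infer that consultations will enter the primary model and bias it materially; the documents do not support that. What stands is that the two sections are not reconciled, and that the prior-trial remark concerns transplant clinicians and not referrals made by palliative care clinicians.

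**On strata,** the harm is conservative and depends on blocking and prognostic strength, neither of which is given. Section 9.7 times the week-2 assessment by type (day +5 autologous, day +8 allogeneic) to catch peak severity in each. That may weaken the link between type and the week-2 score. These points limit the size; they do not justify leaving the strata out. Interaction models normally carry main effects too, but those planned here are conditional or exploratory and are not the primary comparison.

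**On the imbalance clause,** a reader might infer inflated type I error. Simulation (324 patients, 18 candidate covariates, r = 0.5) gave 3.7–5.2% for any single rule. Reporting the most favourable of three or four rules gave 5.6–8.7%, but the plan nowhere says rules would be chosen after seeing results. By itself, the absent list and criterion is missing detail.

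**Conclusion.** The point holds in two limited parts. First, the stratifiers should be main effects of the primary model. Omitting them costs an interval about 3–12% too wide, type I error of 4.4% down to 2.8%, and about 0.5–3.5 points of power. All of this is conditional on blocking and on the strata explaining 5–20% of the variance left after baseline. The error is on the conservative side. It would be wrong to read it as a fault in the sample size, since the 87% reproduces and is not undermined.

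Second, the status of social work consultations is unresolved between Sections 9.3 and 10.1. The possible bias follows the product in Step 4. The 0.6-point shift and roughly 6% error rate only illustrate it, because the arm difference in consultation is unknown and could be nil.

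Confidence is high on what the text does and does not plan, and lower on the magnitudes, which rest on assumed inputs. The change should be made because it costs almost nothing.

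**What to change.** - Specify the primary model as week-2 FACT-BMT on arm, baseline FACT-BMT, study site and transplant type. Use the same stratifier terms in the patient secondary regressions and the mixed models.
- Move imbalance-driven adjustment to a labelled sensitivity analysis limited to baseline variables.
- State that social work consultations and other post-randomisation variables are not covariates in the treatment-effect models, and report consultations by arm. Hospital length of stay, which Section 9.5 lists among characteristics collected at baseline, belongs with these.
- Reconcile Section 21.0 (site only) with Sections 3.0, 5.1 and 9.1 (site and transplant type), so that the model matches the randomisation actually used.

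**Cost:** wording only, with no new data. Site takes 2 degrees of freedom and type takes 1, so 321 becomes 318. If the strata explain nothing, the interval widens by at most about √(321/318) − 1 = 0.5%.
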